Official Title: The Effect of a Gait Modification Training Program on Impact Loading and Running-related Injuries

NCT Number: NCT03302975

The Effect of a Gait Modification Training Program on Impact Loading and Running-related Injuries

Objectives

The purpose of this study is to determine whether a gait modification training program can result in a reduction in impact loading and the incidence of running-related injuries (RRI) among recreational distance runners. Knee angle at initial contact (IC) has been identified in a previous study by the principal investigator (pre-submission stage) as both increasing the average vertical loading rate (AVLR) and the incidence of RRI in the female recreational running population. This variable will be modified to determine the effect on impact loading (AVLR) and incidence of RRI using a repeated measures design.

Background

Numerous studies have shown that individuals can be trained to modify aspects of walking and running[1-18]. Moreover, gait retraining has been shown to be effective in treating overuse injuries in runners[4,7,8,18]. However, since it is unclear what variables independently contribute to the recovery from these injuries and whether these variables can be manipulated prospectively to reduce the risk of injury, optimal prevention and treatment of RRI remains unknown. These studies all included some form of feedback to the subjects, which helped them modify their technique. The feedback methods included verbal instructions and real-time visual[1,3,6,7,9,12,17,18] or auditory information[4,5,8,11,15,16]. Other studies used verbal instructions and videotape reviews[13,14] or an extensive training program[8,19]. Many of these studies have used

overlapping instructions and feedback which make it difficult to infer which factors had a causative effect on changing gait mechanics, muscle activation patterns, and ground reaction forces. Others have used feedback that is difficult to reproduce outside of a lab or clinic environment. Simple cues that produce a specific and intended kinematic or spatiotemporal modification are necessary. Furthermore, these cues need to be consistent and reproducible in multiple training environments in order to be retained as part of the motor program.

Arendse et al[19] reported that 7.5 hours of training over 5 consecutive days was required to learn FF landing, while Dallam et al[20] reported a 1-hour session for 12 weeks was necessary. Diebal et al showed FF landing could be trained in 6 weeks, with training sessions 3 times per week for 45 minutes[8]. An 8-session faded-feedback approach was used by Barrios et al to retrain walkers. This design produced changes in lower extremity biomechanical variables immediately post-intervention as well as at 1-month follow-up [1]. Subjects who receive intermittent feedback have been shown to perform better in the long-term than subjects who receive continuous immediate feedback[21,22]. Removing the feedback is beneficial to motor skill learning because the subjects must rely on internal cues for performing correct motor patterns[23].

Some researchers have suggested that further studies should investigate the effect of gait retraining on injury prevention in runners[8,19]. Changing a runner's gait to reduce the risk of a certain injury, however, may have unintended consequences such as increasing the chance of another kind of injury if other kinematic or spatiotemporal variables are adversely impacted[2,19]. Knowledge of the independent contributions of identified kinematic and spatiotemporal risk factors to impact loading and injury

incidence will allow for targeted modification of these variables so that the risk of negative consequences is limited.

Hypotheses

It is hypothesized that after a 15-week training program, a change in knee flexion at IC will be significant ($p < 0.05$) and will result in decreased impact loading (AVLR) and incidence of RRI.

Outcome Measures

Primary outcome measures:

- 1) Kinetic outcomes: Average vertical loading rate (Body weights [BW] per second) and vertical impact peak (BWs).
- 2) Incidence of RRI (calculated as the number of new injuries reported per 100 runners at risk).

Secondary outcome measures:

Secondary outcome measures will be kinematic and/or spatiotemporal correlates of impact loading and incidence of RRI as guided by the literature and determined in previous studies.

- 1) Knee flexion angle at IC
- 2) Peak knee flexion angle
- 3) Angle of the shank at IC

Other outcome measures:

Other outcome measures will be collected to describe and assess the success of the gait modification intervention. These measures include:

- 1) Participant compliance: Participant compliance with the gait modification intervention will be measured by the number of training sessions attended at Fortius (to a maximum of 8, converted to a percentage) and the number of home training sessions completed (to a maximum of 22, converted to a percentage). Participants will record their home training sessions in their weekly online questionnaire.
- 2) Adverse events: Adverse events experienced due to the intervention (i.e. increased pain or a new injury) will be recorded in the weekly online questionnaires.
- 3) Fidelity of training sessions: Assessed by calculating the difference (error, in degrees) between the intended target angle and the actual angle produced during the 10 consecutive stance phases at each of the four time points during each training session (first min, 33%, 66%, and last min) and averaged within the session.
- 4) Perceived difficulty in achieving targeted modification: Assessed at each training session using an 11-point numerical rating scale (NRS) (0 = “no difficulty”, 10 = “unable to perform”).
- 5) Pain: Assessed at each training session using an 11-point NRS (0 = “no pain”, 10 = “worst pain imaginable”).
- 6) Rating of Perceived Exertion (RPE): Assessed at each training session using the 15-point Borg RPE scale.

- 7) Anthropometric and functional measurements: These will include BMI, navicular height, hip internal/external rotation range of motion, Q-angle, and weight-bearing ankle dorsiflexion and knee valgus angle.

Methods

The proposed study is a repeated measures design. A sample size calculation for comparing injury incidence is based on our current injury rate (27.9%) in our previous studies. We calculate that we will require a sample size of 30 to achieve a minimum power of 80% ($\alpha = 0.05$). Thirty uninjured female recreational runners will be recruited through advertisements in Vancouver-area running clinics. Participants must be female between the ages of 18 and 60; have been running for at least three months prior to study commencement; and have experience with running on a treadmill. Participants must not have run more than two half marathons previously. Participants will be excluded if they have experienced a lower extremity injury in the prior three months; have undergone hip, knee, or ankle joint surgery; or currently have pain in their lower back or lower extremities while running.

Eligible participants will first be screened for the biomechanical trait in question (less than 10° of knee flexion at IC). A historical control group from a previous study will be used as a comparison group and a sample that meets the same screening criteria will be matched for age and BMI.

Demographics and a detailed training and injury history will be taken for each subject, which will include information on running experience, previous best times at 5km, 10km, half marathon and marathon distances (if available), and overall number and

type of general musculoskeletal and/or running injuries. Anthropometric and functional measurements (including height, mass, foot length, navicular height, hip internal/external rotation range of motion, Q-angle, and weight-bearing ankle dorsiflexion) will be collected prior to treadmill testing for descriptive purposes and for use as covariates. Participants will wear their regular running shoes.

[figure not shown]
Using an eight-camera passive marker system (Qualisys Motion Capture Corp., Gothenburg, Sweden) and Visual 3D software (C-Motion, Inc., Germantown, MD), participants will undergo a static calibration trial to form a musculoskeletal model. Anthropometric properties of body segments will be scaled to each individual using the subject's height, mass, and segment lengths. Each model segment position will be multiplied by the respective mass; these numbers will then be summed and divided by the total body mass. For bilateral analysis, 19 static/calibration markers and 42 tracking markers (total = 61) will be affixed to each subject. Before data collection, each subject will be allowed 5 minutes to warm-up and determine their speed. Participants will be able to adjust the speed as needed over this period until they identify a speed that is representative of a typical moderate intensity run. Participants will then be asked to identify their rating of perceived exertion (RPE) using Borg's RPE scale [33]. The speed will be adjusted until the participant is at an RPE of 13 ("Somewhat hard" or 70% effort). Three-dimensional kinematic and spatiotemporal data will be collected at this pace over three trials of 15 seconds using the six-camera, three-dimensional motion analysis system. Kinetic data will be collected using an embedded force platform in the instrumented treadmill. All kinetic variables will be normalized to subject body mass. Initial contact and toe-off will be identified by force plate data (using a threshold of 50N).

These data points will be used to determine the stance and swing phases of the gait cycle. All outcome measures will be determined by averaging the first 10 consecutive stance phases within each of the three trials ($n = 30$ total stance phases). For the purposes of comparison between RF strikers and MF/FF strikers (who may not display a clear VIP), AVLR will be calculated for all individuals as the slope of the vertical GRF–time curve from IC to 13% of stance. This time value has been shown to be the best surrogate for the timing of a missing VIP.

Participants will follow a 15-week half-marathon training program, wearing their regular running shoes throughout the study. During the training program, participants will attend the Fortius Biomechanics Lab on Weeks 1, 2, 4, 6, 8, 10, 12, and 14 (eight sessions in total) for a 15-30 minute gait modification training session following a faded-feedback design (figure 1)[1]. The aim of these sessions will be to modify the angle of knee flexion at IC so that it is greater than 10 degrees. Gait modification will be facilitated through the use of real-time biofeedback of performance[1,24,25] at each training session. The co-investigator, a sport physiotherapist, will also provide standardized verbal instructions to change the desired biomechanical outcome (e.g. “Land with a more bent knee”). For the first four sessions, participants will receive feedback for 100% of the session. By the eighth session, feedback will be provided for just 10% of the session (minutes 1, 15, and 30). All participants will have a total of 60 running sessions (four times per week for 15 weeks). During the weeks in which a lab-based gait modification session is scheduled, participants will have one lab-based biofeedback session and three “regularly scheduled” run sessions in which they will be instructed to focus on the same cues given in the lab during their runs. During the weeks in which no lab-based feedback session is scheduled,

participants will only have the four “regularly scheduled” run sessions in which they will be instructed to focus on the same cues given in the lab during their runs. This will ensure that they do not have any more run sessions than the historical control group.

Figure 1. Faded-feedback design depicting time spent running on the treadmill during each session and time with visual real-time biofeedback for each session. For the first four sessions, participants will receive feedback for 100% of the session. By the eighth session, feedback will be provided for just 10% of the session.

Kinetic, kinematic, and spatiotemporal data will be collected during each session to ensure that the goal of the intervention is being achieved. This will be assessed by calculating the difference (error, in degrees) between the intended target angle and the actual angle produced during the 10 consecutive stance phases at each of four time points during each training session (first min, 33%, 66%, and last min) and averaged within the

session.

Pain, RPE, and perceived difficulty in achieving the targeted modification will be measured in all training sessions using an 11-point NRS (pain and perceived difficulty) and the Borg RPE scale. Adverse events (increased pain or a new injury) and participant compliance with the gait intervention will be assessed in the weekly online questionnaire.

All participants will return to the Fortius Biomechanics Lab at the conclusion of the 15-week half-marathon clinic for retesting. A one-month post-test will also be performed to assess for retention. During both sessions (follow-up and retention), the participants will be asked to run naturally and then with the modified pattern. The natural pattern will be collected to determine whether it has changed since baseline.

The verbal instruction during each training session will be given by the principal investigator (a sport physiotherapist with clinical experience in gait retraining). The therapist will not be involved in data collection, but will process the data. To ensure blinding, data will be collected by an independent lab assistant and coded to blind for participant number for later processing and analysis by the principal investigator. This process will ensure that the principal investigator is unaware of which participant they are analyzing until the conclusion of the study.

Demographic, anthropometric, and functional variables will be analyzed for differences between the intervention group and a historical control group from our previous studies at baseline using 2-tailed t-tests for normally distributed continuous variables. Injury incidence (number of new injuries reported per 100 runners at risk) will be compared between groups using paired t-tests. Differences in outcomes pertaining to the feasibility of the intervention (perceived difficulty, exertion, fidelity, compliance) will

be assessed in the intervention group between session 1 and 8 using paired t-tests. The biomechanical and clinical outcomes from the follow-up and one-month post-intervention modified patterns will be compared to the baseline values using ANOVAs for repeated measures. Planned pairwise comparisons between the visits will be conducted. Differences will be considered statistically significant at $p < 0.05$. All statistical analyses will be performed using SPSS version 22.0 (SPSS Inc., Chicago, IL).

References

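### Home compliance is scored out of 22, a number that cannot be traced to the 52 cued runs scheduled outside the lab, and compliance has no session-level value for its planned paired t-test

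*Combined protocol and SAP*

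**What the plan says.** The Outcome Measures section (other outcome measures, item 1) defines participant compliance with the gait intervention as two percentages. One is for lab attendance: "the number of training sessions attended at Fortius (to a maximum of 8, converted to a percentage"). The other is for practice outside the lab: "the number of home training sessions completed (to a maximum of 22, converted to a percentage"). On data collection it says: "Participants will record their home training sessions in their weekly online questionnaire".

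The Methods section sets out the running schedule:

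- Total: "All participants will have a total of 60 running sessions (four times per week for 15 weeks").
- Lab visits: "on Weeks 1, 2, 4, 6, 8, 10, 12, and 14 (eight sessions in total").
- In a week with a lab visit, "participants will have one lab-based biofeedback session and three" regularly scheduled runs.
- In a week without one, "participants will only have the four" regularly scheduled runs.

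In both kinds of week, runners are told to concentrate on the lab cues during the runs outside the lab. The schedule is also meant to keep their number of runs from exceeding that of the historical control group.

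The statistical paragraph at the end of Methods lists compliance with perceived difficulty, exertion and fidelity as feasibility outcomes. All four are to be compared between session 1 and session 8 by paired t-tests in the intervention group.

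**The concern.** A compliance percentage needs a denominator that a reader can tie to what participants were asked to do. The only gait practice outside the lab that the protocol describes is the set of cued runs in the weekly schedule, and there are far more than 22 of them. Methods never uses the term home training session, and Outcome Measures does not define it. A runner filling in the questionnaire, or an analyst computing the percentage, could not tell which runs count.

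The t-test is a separate defect in the same outcome. A paired test needs one value per runner at each of two occasions, but the definition gives one lab percentage and one home percentage per runner for the whole programme.

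What is at stake is the description of feasibility. These measures are collected to show whether the intervention was delivered and taken up, and an adherence figure of unclear meaning does not help with that.

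**Working it through.** **Inputs.** From Outcome Measures: home maximum 22, lab maximum 8. From Methods: 15 weeks, 4 runs a week, lab visits in Weeks 1, 2, 4, 6, 8, 10, 12 and 14, with 3 non-lab runs in a lab week and 4 in any other week.

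**Step 1: the schedule.**
- Total runs: 15 × 4 = 60, as stated.
- Lab weeks: 8, as stated. Other weeks: 3, 5, 7, 9, 11, 13 and 15, which is 7.
- Non-lab runs in lab weeks: 8 × 3 = 24.
- Non-lab runs in other weeks: 7 × 4 = 28.
- All non-lab runs: 24 + 28 = 52, which agrees with 60 − 8.

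The totals of 60 and 8 reproduce. The 22 does not.

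**Step 2: is 22 some part of the schedule?**
- Lab-week runs give 24; other-week runs give 28.
- Methods marks off one further phase: "For the first four sessions, participants will receive feedback for 100% of the session". Those sessions fall in Weeks 1, 2, 4 and 6. Non-lab runs in Weeks 1 to 6 are 4 × 3 + 2 × 4 = 20. Weeks 7 to 15 give 4 × 3 + 5 × 4 = 32.
- No block of consecutive whole weeks gives 22. Six-week blocks total 20 or 21, and seven-week blocks total 24 or 25.
- For a fixed count of *a* home sessions per lab week and *b* per other week, solve 8*a* + 7*b* = 22 with *a* from 0 to 3 and *b* from 0 to 4. The only solution is *a* = 1, *b* = 2 (8 + 14 = 22). This is the same as two gait sessions a week including the lab visit: 2 × 15 − 8 = 22. The documents do not state that rule.

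Scattered weeks can also be made to add to 22 (six lab weeks and one other: 6 × 3 + 4), but nothing in the text names such a set.

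**Step 3: consequence under each reading.**

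| Reading of the 22 | Result |
|---|---|
| All cued non-lab runs are counted against 22 | 22 of 52 runs (22/52 = 42.3%) scores 100%; all 52 runs would score 52/22 = 236% unless capped |
| 22 is an intended subset | No inflation; 52 − 22 = 30 runs (30/52 = 57.7%) lie outside the score; lab and home scores together cover (22 + 8)/60 = 50% of scheduled runs |

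**Step 4: the session 1 versus session 8 test.** Neither whole-programme percentage has a value at session 1 or at session 8. Two substitutes can be imagined:
- *Attendance at the session.* Every runner seen at both sessions scores the same at each, so every difference is zero and there is no variance to test.
- *Home runs in the week of the session.* Sessions 1 and 8 fall in Weeks 1 and 14, both lab weeks. The score would be out of 3 in each week under the Methods schedule, or out of 1 under the one-and-two rule of Step 2. The weekly questionnaire might supply it, but the plan does not define it.

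**The case against.** The strongest reply is that a contradiction needs two statements about the same quantity. Outcome Measures counts home training sessions and Methods counts regularly scheduled runs, so a maximum of 22 inside a total of 52 is not a contradiction unless every non-lab run is a home session, and no sentence says so. The protocol recruits through running clinics and calls the programme a half-marathon clinic, so some scheduled runs may be clinic runs. Suppose, as an assumption the documents do not state, that two runs each week are clinic runs (30 in all). That leaves one home run in each lab week and two in each other week, which is 22, and 8 + 30 + 22 = 60 fits the schedule exactly.

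Much of this stands. A reader might infer that 22 is a proven error; the documents do not support that, because an unstated subset remains possible. A reader might also take 42.3% reported as 100% to be an expected bias, but it follows only if all cued runs are counted against 22. And a reader might say that under the subset reading 30 runs go unmeasured. The questionnaire's content is not given, so the most that can be said is that they lie outside the compliance score.

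It does not rescue the definition. The clinic-run split appears nowhere in the text, and the runs it would exclude carry the same cue instruction as those it would keep. A figure is missing from the copy reviewed and could not be checked, but the caption of Figure 1 concerns treadmill and feedback time in the lab sessions, and Methods gives the run schedule in words.

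On the t-test, it is fair to say that a weekly home score could be defined instead of dropping the test. That still requires a definition the plan lacks.

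**Conclusion.** The point holds as a minor one. The home denominator of 22 cannot be traced to any grouping the documents state, the term it counts is undefined, and the schedule contains 52 cued runs outside the lab. Whether 22 is an error or an unstated subset cannot be settled from the text. The size depends on that: either a runner at 42.3% of the cued runs can read as 100%, or there is no inflation and 30 of the 52 cued runs are left out of the score. The count of 52 assumes only that the schedule in Methods is followed as written.

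The second part does not depend on the first. Whatever the denominator, compliance as defined has no session-level value, so its paired t-test cannot be run.

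The effect stops at the reported compliance figures. No primary or secondary analysis uses them.

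**What to change.** 1. Define a home training session, and report home compliance as cued non-lab runs completed out of the 52 scheduled. This is the full set to which the cue instruction applies.
2. Word the weekly questionnaire so that it asks for all non-lab cued runs.
3. If 22 is an intended subset, name those runs in the Methods schedule and report that percentage alongside the one out of 52. This keeps the planned measure while making clear what it covers.
4. Remove compliance from the session 1 versus session 8 paired t-tests and summarise lab and home compliance descriptively. Keep the tests for perceived difficulty, exertion and fidelity, which are assessed at each training session.

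The cost is one definition, one denominator, one word removed from the analysis text and perhaps a small change to the questionnaire. The questionnaire change is best made before data collection, since runs that were not asked about may not be recoverable. The downside is that reported home compliance may be lower. Design, sample size and the primary and secondary analyses are unaffected.

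### The claimed 80% power for injury incidence names no target rate; at 27.9%, 30 v 30 two-sided, it needs a fall to about 1-4%

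*Combined protocol and SAP*

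**What the plan says.** The Methods section says the sample size for comparing injury incidence is "based on our current injury rate (27.9%) in our previous studies". It continues: "We calculate that we will require a sample size of 30 to achieve a minimum power of 80" per cent, with alpha 0.05, and then "Thirty uninjured female recreational runners will be recruited".

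The other inputs a power calculation needs would have to come from elsewhere in the document:

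- **Effect.** The Hypotheses section gives a direction only: a change in knee flexion "will result in decreased impact loading (AVLR) and incidence of RRI".
- **Outcome.** Outcome Measures lists as primary "Incidence of RRI (calculated as the number of new injuries reported per 100 runners at risk"; this counts injuries, not injured runners.
- **Comparator.** Methods states "A historical control group from a previous study will be used as a comparison group". Controls have to pass the knee-flexion screen too, and matching is on age and BMI. The number of controls is not given.
- **Test.** The analysis paragraph of Methods names paired t-tests for injury incidence. Two-tailed testing is mentioned only for the comparison of groups "at baseline using 2-tailed t-tests for normally distributed continuous variables".

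**The concern.** Power for a comparison of two rates depends on both rates. Only one is given, yet 80% is called a minimum, as if it were a property of 30 runners whatever the effect. Injury incidence is a primary outcome and the only outcome with a sample-size justification. A reader who accepts the floor could take a non-significant result as evidence that gait retraining does not prevent injury, when the trial may have had little chance of detecting even a large benefit.

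The reference rate is a second difficulty. It comes from previous studies in general, whereas both groups here are restricted to runners with less than 10 degrees of knee flexion at contact. The Objectives link knee angle at contact to injury, so 27.9% may not be the incidence to expect in the controls.

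**Working it through.** **Inputs from the plan:** reference rate p1 = 0.279, n = 30, alpha 0.05, power 0.80, paired t-test.

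**Assumptions (not in the plan):** 30 matched controls, two-sided test, at most one injury counted per runner, control incidence equal to 27.9%. The halving to p2 = 0.1395 is an illustrative benchmark.

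**1. Can the stated figure be reproduced?** Not directly, because p2 is missing. The available check is to solve for the p2 at which n = 30 gives 80%. With the usual pooled normal formula,

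power = Φ{[(p1 − p2) − 1.96·√(2p̄(1 − p̄)/n)] / √([p1(1 − p1) + p2(1 − p2)]/n)}, where p̄ is the mean of p1 and p2.

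- p2 = 0.0245: (0.2545 − 1.96 × 0.0926)/0.0866 = 0.84, so power is 80%.
- p2 = 0.1395: (0.1395 − 1.96 × 0.1050)/0.1035 = −0.64, so power is 26%.

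This formula therefore returns 30 per group only for a fall from 27.9% to about 2.5%. If 30 were the total (15 v 15), two-sided power would be 41% (Fisher) to 64% (chi-square) even with no injuries at all in the intervention group.

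**2. Exact enumeration, 30 v 30, two-sided.** Fisher and chi-square sum over all pairs of binomial counts. For the paired t-test, let p11 be the probability that both members of a pair are injured: p11 = p1p2 + ρ√(p1(1 − p1)p2(1 − p2)). Then enumerate the 30 pair differences, with probability p1 − p11 of +1 and p2 − p11 of −1. At ρ = 0 and p2 = 0.03, these are 0.271 and 0.022, and power is 80.3%.

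| Test | Rate needed for 80% | Relative reduction | Power for a halving |
|---|---|---|---|
| Fisher | 1.1% | 96% | 17% |
| Paired t, ρ = 0 | 3.0% | 89% | 23% |
| Chi-square | 3.7% | 87% | 26% |

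Expected injured runners: 30 × 0.279 = 8.4 controls against 30 × 0.0113 = 0.3 to 30 × 0.0374 = 1.1 intervention runners.

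**3. More favourable readings, still at 27.9%.**

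| Reading | Rate needed for 80% | Power for a halving |
|---|---|---|
| One-sided, 30 v 30 | 2.8-5.7% | 26-39% |
| 2-4 controls per runner, two-sided | 4.4-8.0% | 28-45% |
| 2-4 controls per runner, one-sided | 5.7-9.6% | 35-57% |
| Paired t, ρ = 0.3, two-sided / one-sided | 6.1% / 7.8% | 32% / 47% |
| Paired t, ρ = 0.5, two-sided / one-sided | 9.4% / 11.0% | 45% / 59% |
| Fixed 27.9% reference (one sample) | 7.8-10.5% | 38-59% |

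The least demanding entry is about 11%: 1 − 0.1095/0.279 = 61% reduction. A one-sample Wald formula with its variance taken at the intervention rate would give 12.8% one-sided, but its rejection region (5 or fewer injured) has a true alpha of 0.118, so it is not counted.

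**4. Exceptions found.** A halving reaches about 80% in two cases: a one-sided paired t-test at the largest possible pair correlation (0.65; 81%), and a one-sided test with correlation 0.5 and four controls per runner (about 80%, by approximation). These require 100% and 84% of injured intervention runners to be paired with an injured control, against 28% if matching carries no information.

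**5. Counting injuries, as the outcome definition is worded.** With Poisson counts assumed, 30 v 30 and two-sided, 80% power needs 0.5 per 100 (conditional exact) or 1.6 per 100 (paired t, simulated). A halving has 14-19% power.

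**6. Precision.** For 8/30 v 4/30 injured, the Wilson intervals are 0.142-0.444 and 0.053-0.297. The Newcombe interval for the difference of 0.133 runs from 0.133 − √(0.125² + 0.163²) = −0.07 to 0.133 + √(0.178² + 0.080²) = 0.33, treating the groups as independent.

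**The case against.** The strongest reply is that nothing stated has been shown to be wrong. The investigators may have used a target rate that was not written down, and some target does give 80% with 30. The group sizes, sidedness and halving above are mine, and the plan never claims a halving, so 17-26% is not the trial's power. All of this stands, which is why the conclusion is that the figure is unsupported rather than miscalculated.

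The figures above also hold control incidence at 27.9%. If low knee flexion raises injury risk, as the Objectives suggest, the controls could have a higher rate, and that would help the plan. Taking illustrative control rates, 30 v 30 two-sided, Fisher to chi-square:

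- 40%: rate needed 7.7-9.9%; power for a halving 30-39%.
- 50%: rate needed 14.3-16.7%; power for a halving 41-52%.

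So the 11% bound belongs to 27.9% and is not general. Even at these higher rates, the reduction needed is about 67-81%, and a halving stays well below 80%.

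That age and BMI matching could not produce the pair correlations in the exceptions is a judgement; the document gives no injury risk by age or BMI. The kinetic primary outcomes have their own repeated-measures analysis and do not depend on this calculation. Neither point supplies the missing target rate.

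**Conclusion.** The concern holds. The 80% cannot be derived from what the plan states, and it is not a floor. With 27.9% in controls, 30 v 30, two-sided 0.05 and at most one injury per runner, it holds only for a reduction of about 87-96%, roughly 8 injured controls against 0-1 injured intervention runners. An illustrative halving would be missed about three times in four or more. Relaxing one of these assumptions at a time, with pair correlation up to 0.5, still leaves a reduction of about 61% or more. The only routes found to 80% for a halving combine one-sided testing with pair correlation of 0.5 or more, which matching on age and BMI alone makes implausible. This should be corrected before the power statement is relied on, because it governs how a null injury result will be read.

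**What to change.** Replace the unconditional power sentence with a conditional one:

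> *With 30 runners and [number] historical controls, counting [runners injured / injuries], control incidence 27.9%, intervention incidence [x], [test], [one/two]-sided alpha 0.05, power is [y].*

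Fill it with the inputs originally used and the power they give, or with recomputed ones. For example, for 30 v 30, a two-sided paired t-test and uncorrelated pairs:

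- counting injured runners: 80% for a fall to 3%, and 23% for a halving;
- counting injuries (Poisson assumed): 80% for a fall to 1.6 per 100, and 19% for a halving.

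Add a sentence that 27.9% comes from previous studies in general and may not apply to runners screened for less than 10 degrees of knee flexion. Add to the analysis paragraph that the between-group difference in injury incidence will be reported with a 95% confidence interval.

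The cost is rewording the sample-size paragraph and one reporting sentence. The stated power for injury becomes less favourable. The primary outcomes stay as listed and no extra recruitment is proposed.
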